7.5.3 Entire Study Termination

The entire study may be suspended or terminated by the Sponsor for safety or other unanticipated reasons or upon request of regulatory agencies. Criteria for premature study termination or suspension are detailed in [Section 14.1, Criteria for Premature Termination or Suspension of the Study](#).

7.5.4 Individual Study Site Termination

Study participation may be suspended or terminated at an individual investigational site for various reasons. Criteria and procedures for premature termination or suspension of an investigational site are detailed in [Section 14.2, Criteria for Premature Termination or Suspension of Investigational Study Sites](#) and [Section 14.3, Procedures for Premature Termination or Suspension of the Study or Investigational Sites](#).

7.5.5 Individual Subject Discontinuation

During this study, it is anticipated that some subjects may permanently discontinue study medication (vadadustat or darbepoetin alfa) for any of the following reasons:

- Unacceptable toxicity or drug intolerability
- Investigator discretion
- Subject withdrawal of consent
- Subject becomes pregnant
- Receipt of a kidney transplant

- Lack of efficacy
- Other reasons.

Lack of efficacy is defined as inadequate response to darbepoetin alfa or vadadustat in the Investigator's opinion.

Subjects who undergo a solid organ (including kidney), hematopoietic stem cell, or bone marrow transplantation will have their study medication (vadadustat or darbepoetin alfa) permanently discontinued.

See [Section 9.4, Study Medication Stopping Rules](#) for additional details on the management of subjects with ALT and AST abnormalities.

It is important to continue to follow subjects that permanently discontinue study medication. Please see Sections 7.5.5.1, Temporary Interruption of Study Medication and 7.5.5.2, Permanent Discontinuation of Study Medication and [Appendix A: Schedule of Activities](#)).

Receipt of rescue therapy is not a reason for permanent study medication discontinuation. While receiving ESA rescue, subjects must temporarily discontinue study medication (vadadustat or darbepoetin alfa), but should resume study medication once rescue therapy has ended, as detailed in [Section 8.4.7, Rescue Therapy](#).

As part of the informed consent process, only subjects who fully understand and agree to full participation and long-term follow-up should be consented to participate.

7.5.5.1 Temporary Interruption of Study Medication

Subjects who temporarily interrupt study medication (vadadustat or darbepoetin alfa) treatment after the first dose and prior to completion of the study will continue with study visits and assessments. Unless contraindicated, treatment should be resumed wherever possible and routinely considered at every visit following study medication discontinuation. If a subject does not return for a scheduled visit, every effort should be made to contact the subject. If a subject's study medication has been temporarily interrupted for more than 60 days, the Investigator should contact the Medical Monitor before resuming study medication.

7.5.5.2 Permanent Discontinuation of Study Medication

Subjects who permanently discontinue study medication prior to global study completion are expected to continue to be followed post discontinuation of study medication. These subjects are to have their EOT visit at the time of permanent discontinuation of study medication, have the Follow-up visit 4 weeks after EOT visit and continue to be followed through global study completion. At global study completion, each subject will have an End of Study (EOS) assessment to complete participation in the study. Receipt of rescue therapy is not a reason for permanent study medication discontinuation. While receiving ESA rescue, subjects must temporarily discontinue study medication but should resume study medication following the end of rescue therapy.

For subjects who permanently discontinue study medication, the Investigator will resume standard of care treatment, including ESAs and iron therapy, as deemed appropriate.

It is important to continue to follow subjects that permanently discontinue study medication.

7.5.5.3 Complete Withdrawal from Further Study Visits/Assessments

A subject has the right to withdraw consent for participation in the study. Withdrawal of consent is a subject's refusal of ALL methods of follow-up noted in the informed consent form: procedures, participation in reduced procedures/study visits, telephone contact only or alternative contact only, source document or designated alternative contact, or access to medical records from alternative sources.

It is important to provide options for the subject to consider for long-term follow-up before the subject withdraws consent. It is important for the Investigator to review options with a subject that would allow follow-up through global study completion before the subject withdraws consent. For subjects considering withdrawal of consent, the Investigator should consult with the Medical Monitor to ensure all options have been explored and that there is complete understanding by the subject for what constitutes withdrawal of consent.

7.5.5.4 Procedures to Support Continued Study Participation

As part of the informed consent process, only subjects who fully understand and agree to full participation and long-term follow-up should be consented to participate. **It is important that subjects understand the long-term duration and purpose of a cardiovascular outcome trial and that the subject (or designee) continue to allow follow-up through global study completion which could be several years, even post subject's permanent discontinuation of study medication.**

In all cases of impending study medication discontinuation or subject request for stopping study visits, the Investigator will discuss with the subject their options of continuing in the study.

It is important to continue to follow every randomized subject, even if discontinued study medication, through global study completion at a frequency and approach that is agreed to between the Investigator and subject. Visit schedule and assessments are flexible and at the discretion of the Investigator and subject and will be clearly documented in the medical chart. Optimal data collection would include the following assessments through global study completion.

- EOS subject status (must collect at minimum)
- MACE Endpoint Questionnaire
- AE Assessment

The protocol allows flexibility of follow-up to maintain the subjects in active status post permanent discontinuation of study medication. For those subjects who decline full participation in the study post discontinuation of study medication, other options for continued follow-up on a subject include (but are not limited to):

1. Reduced frequency of on-site visits
2. Telephone visits in lieu of on-site visits
3. Telephone or any contact method (e.g., email, site staff visit subject's home, etc.) to verify vital status
4. Telephone or any contact method with an alternative person (family member or medical designee)

5. Study team access to medical records for reporting MACE data or vital status

In the most extreme case, the protocol will accommodate minimal contact with a subject or alternative method to obtain the subject's vital status. The objective is to **keep a subject's study status active** to ascertain at a minimum vital status (alive or deceased) at the global study completion.

The Investigator will ensure understanding and documentation of the reason(s) for a subject's desire to stop study procedures or stop study medication.

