7.5.2 Subject Completion

A subject will be considered as having completed the study, regardless of whether they are on or off study medication (vadadustat or darbepoetin alfa), if the subject is followed until global study completion (end of trial).

The table outlines the different categories of subjects and handling the global study completion activities.

Subject Status at time of Global Study Completion	End of Treatment (EOT)	End of Study (EOS)
Subject on study medication (includes those on temporary interruption)	After announcement of global study completion: 
 • Perform EOT visit • Perform the Follow-up visit 4 weeks after EOT visit and include End of Study (EOS) subject status 	Not applicable The EOS subject status will be captured as part of the Follow-up visit
Subject permanently discontinued study medication and continues to be followed in the study	At time of permanent discontinuation of study medication: 
 • Perform EOT visit • Perform the Follow-up visit 4 weeks after EOT visit 	Optimal data collection would include the following assessments: 
 • EOS subject status (must collect at minimum) • MACE Endpoint Questionnaire • AE Assessment
Subject Lost to Follow-up	Not applicable	Work with third party vendor to ascertain vital status and complete EOS subject status

		If subject-site contact is reestablished and possible, collect available information for EOS subject status
Subject Withdrawn Consent	Not applicable	Complete the EOS subject status form at time of withdrawal of consent, absolute refusal of ALL methods of MACE and health status follow-up
Subject Death	Not applicable	Complete the EOS subject status form at the time of death (see Section 10 Adverse Events for more details on other actions related to reporting a death)

The need for rescue therapy does not constitute study completion and is not a criterion for subject withdrawal from the study. Also, the occurrence of a safety endpoint, or if a subject progressed to chronic dialysis dependent CKD (DD-CKD), does not constitute study completion and is not a criterion for subject withdrawal from the study or study medication (vadadustat or darbepoetin alfa).

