9.2 Study Procedures and Evaluations

9.2.1 Clinical Evaluations

The following clinical evaluations will be conducted during the course of the study:

- Medical history, demographics, and physical examination: Medical history, demographic information, and physical examination (including height) will be collected at SV2. Relevant medical history (with particular emphasis on previous medical conditions that may lead to exclusion) and significant ongoing medical conditions or diseases should be documented. After SV2, an abbreviated, symptom-directed physical examination should be performed at the discretion of the Investigator as clinically indicated.
- Vital signs: Vital signs will include heart rate and blood pressure. Heart rate and blood pressure should be assessed in the seated position after 5 minutes of rest. Vital signs will be collected at SV1, SV2, Baseline, during study visits, and EOT and should be taken prior to blood draws when possible.
- Weight: Weight will be collected for all subjects at SV2, at Weeks 12, 24, 36, and 52, yearly thereafter, and at the EOT visit. For subjects on darbepoetin alfa, patients will be weighed for dosing as per the local standard of care.
- 12-Lead electrocardiogram (ECG): A standard 12-lead ECG will be performed at Baseline. The ECG should be obtained after the subject has been resting comfortably in a supine position for approximately 5 minutes and should be taken prior to vital sign assessments and blood draws when possible. With the subject in a supine position, obtain the 12-lead tracing. All ECGs will be reviewed by the Investigator for the presence of rhythms of potential clinical concern. A record of the tracing(s) will be made and retained with other source documents.
- Completion of MACE Endpoint Questionnaire: At each post-randomization study visit, the subject must specifically be questioned regarding the occurrence of any potential MACE endpoint event since the last study visit. **IMPORTANT: The endpoint questionnaire**

electronic CRF must be completed in full at each visit even if no potential MACE endpoints have occurred. If a potential endpoint event is reported, the date of the event should be recorded and the appropriate source documents should be collected according to the endpoint packet checklist.

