11.1.2 Sample Size for the Primary Safety Endpoint

The primary safety endpoint is the time from randomization date to the first (adjudicated) MACE +1.

The primary safety analysis will be based upon all events that accrue over the 2 NDD-CKD studies (Studies AKB-6548-CI-0014 and AKB-6548-CI-0015). The sample size with respect to the MACE endpoint has been determined based on the number of events needed to demonstrate noninferiority of the 2-sided 95% confidence interval for the hazard ratio (vadadustat/darbepoetin alfa). It has been calculated that 631 events will be required overall to have 80% power to establish noninferiority with a margin of 1.25, and >90% power to establish noninferiority with a margin of 1.3 assuming no difference between treatment groups. The power is >90% to establish a noninferiority margin of 1.25 if the hazard ratio is 0.95 favoring vadadustat. A MACE rate of 10% annually is anticipated in both treatment arms based on a comprehensive review of available epidemiology and prospective clinical studies in the field. The number of MACE in each study will be a function of the actual pattern and size of enrollment as well as the duration of follow-up.

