11.5 Missing Data

Subjects who stop study medication treatment after randomization and prior to completion of the study should continue with planned study visits and assessments unless they withdraw consent for participation in the study. Similarly, subjects will continue with study medication and study procedures following the initiation of rescue therapy, with the exception that the subjects must discontinue taking study medication while receiving an ESA rescue therapy. Treatment with study medication should be resumed after an appropriate interval following the ESA rescue therapy as described in [Section 8.4.7, Rescue Therapy](#). Data will continue to be collected following initiation of the rescue therapy as per the study Schedule of Activities.

All data collected during the study, including at any point after the initiation of rescue therapy as well as after early discontinuation of study medication treatment, will be used for the primary analysis as well as main analyses of all efficacy endpoints. Sensitivity analyses will be performed to assess an impact of rescue therapy on study conclusions.

In the primary analysis of the primary efficacy endpoint, all available qualifying Hb measurements during the pretreatment period and during the primary evaluation period

(Weeks 24-36) will be used to calculate an average Hb during each period, respectively, for each subject. For any subject with no available Hb measurements during the primary evaluation period, multiple imputations will be used to impute the change from Baseline value (details are provided in the SAP). In an analogous manner, an average Hb will be calculated for the secondary evaluation period (Weeks 40-52) for each subject. Given the design of this study where the subjects will continue to be assessed after early study medication discontinuation, it is expected that there will be only a minimal amount of missing data and the primary analysis should not be substantially affected by the imputation.

All data pertaining to the MACE endpoint collected at any point during the study, both during study medication treatment and post study medication treatment discontinuation, and regardless of the rescue therapy, will be used for the primary analysis of the MACE endpoint and its individual components.

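### From four weeks after the End of Treatment visit, the operative sections require only end-of-study status for subjects off study drug, so non-fatal MI and stroke can be captured less completely than death

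*Protocol*

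**What the plan says.** Section numbers refer to Protocol Amendment 7 (Version 8).

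- **Operative follow-up text.** Section 7.5.5.4 lists three items for subjects who have stopped study drug: end-of-study (EOS) status, the MACE Endpoint Questionnaire and AE assessment. Only the first is compulsory: "EOS subject status (must collect at minimum". The visit schedule is left to the investigator and subject. The table in 7.5.2 introduces the same list with "Optimal data collection would include the following assessments". Section 9.3.12 and the synopsis repeat it, and Appendix A footnote [c] repeats the flexibility.
- **Early off-drug contact.** Section 7.5.5.2 expects an End of Treatment (EOT) visit at discontinuation and a Follow-up visit four weeks later. Sections 9.3.9 and 9.3.10 include the MACE questionnaire at both.
- **Visit-based rule.** Section 9.2.1 states: "At each post-randomization study visit, the subject must specifically be questioned regarding the occurrence of any potential MACE endpoint event".
- **Text pointing the other way.** Section 11.5 says subjects who stop drug should keep to planned visits unless they withdraw consent. Section 10.3.1 runs AE reporting from randomization to global study completion. Appendix A footnote [dd] says EOS status for off-drug subjects includes the Follow-up visit activities.
- **Analysis.** Section 11.2 assigns MACE to the randomized population. Section 11.5 uses all MACE data, "both during study medication treatment and post study medication treatment discontinuation". Section 11.7.1 calls this study's MACE result descriptive and places the primary MACE analysis in the pool with Study CI-0015.

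**The concern.** MACE has three components. Off drug, death is the one that the operative text pursues to the end: 7.5.5.5 seeks vital status for every randomized subject, using public records and, if needed, a third-party provider. Non-fatal MI and stroke have to be asked about or found in records, and after the Follow-up visit no operative section requires either.

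The permissive list in 7.5.5.4 stands apart from the step-down options, which are for subjects who decline full participation. It therefore also covers a willing subject.

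If the arms stop drug at different rates, the share of follow-up with weak ascertainment differs by arm, and the observed hazard ratio moves in favour of the arm that stops more. Different rates are plausible: the trial is open-label, compares tablets with injections, and allows discontinuation for lack of efficacy as judged by an investigator who knows the treatment (7.5.5). Sections 6.2 and 8.4.3 rely on an identical assessment schedule in both arms to limit bias, and off drug that schedule becomes a case-by-case agreement. Missed events also slow accrual to the 631 events that close the study, although the target itself does not change.

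**Working it through.** **1. The plan's own figure.** Section 11.1.2 states: "It has been calculated that 631 events will be required overall to have 80% power to establish noninferiority with a margin of 1.25", assuming no treatment difference and judged by "noninferiority of the 2-sided 95% confidence interval for the hazard ratio". With 1:1 allocation and the Schoenfeld formula:

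events = 4(1.960 + 0.842)² / (ln 1.25)² = 4 × 7.849 / 0.0498 ≈ 631.

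This reproduces exactly. Power with 631 events is 80.0% for margin 1.25, 90.9% for margin 1.3, and 93.1% for margin 1.25 at a true hazard ratio of 0.95, which agrees with "The power is >90% to establish a noninferiority margin of 1.25 if the hazard ratio is 0.95 favoring vadadustat". Noninferiority at 1.25 needs an observed hazard ratio of at most 1.25 × exp(−1.96 × 2/√631) = 1.069. No stated figure is wrong; the issue is which events reach the analysis.

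**2. What is required off drug, by time.**

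| Time | 7.5.2, 7.5.5.4, 9.3.12, synopsis | Other text |
|---|---|---|
| EOT and Follow-up four weeks later | Both visits performed | Questionnaire included (9.3.9, 9.3.10) |
| After Follow-up, before global completion | No fixed contact; questionnaire and AE assessment optimal | Planned visits should continue (11.5); AEs reportable (10.3.1) |
| Global completion | EOS status compulsory; questionnaire and AE assessment optimal | EOS includes Follow-up activities, hence the questionnaire (footnote [dd]) |

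Section 9.2.1 does not settle the conflict. It attaches to visits, and Section 9 describes the scheduled treatment-period visits as those made while receiving study medication.

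**3. Size, simple formula.** None of these inputs is in the documents; all are assumptions:
- f, non-fatal share of first MACE: 0.25 to 0.45.
- p, share of person-time with vital status only: 0.20 to 0.30 on vadadustat, 0.15 to 0.20 on control.
- Every non-fatal event in that time is missed.

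Observed HR / true HR = (1 − f·p_v) / (1 − f·p_c)

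| p_v / p_c | f | Ratio | True 1.25 seen as |
|---|---|---|---|
| 0.30 / 0.15 | 0.45 | 0.865 / 0.9325 = 0.928 | 1.16 |
| 0.25 / 0.15 | 0.45 | 0.8875 / 0.9325 = 0.952 | 1.19 |
| 0.25 / 0.15 | 0.25 | 0.9375 / 0.9625 = 0.974 | 1.22 |
| 0.20 / 0.15 | 0.25 | 0.95 / 0.9625 = 0.987 | 1.23 |
| 0.20 / 0.20 | any | 1.00 | 1.25 |

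The full range is 0.93 to 1.00. In the last row nothing is biased, but f·p = 0.05 to 0.09 of events are lost in each arm. If control stops more, the bias reverses: swapping the first row gives 0.9325 / 0.865 = 1.078, and a true 1.25 is seen as 1.35.

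**4. Size, simulation.** This keeps every death, including death after a missed MI or stroke, and counts non-fatal events up to four weeks after stopping. The MACE rate is the plan's: "A MACE rate of 10% annually is anticipated in both treatment arms". Assumed: exponential times, two years of follow-up, non-fatal share 30% to 50%, and 50% to 100% of later off-drug non-fatal events missed. The chance of concluding noninferiority is computed at 631 observed events, as if the same bias applied across the pool.

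| Yearly discontinuation rate, vadadustat / darbepoetin | HR seen at true 1.0 | HR seen at true 1.25 | False noninferiority (nominal 2.5%) |
|---|---|---|---|
| 0.25 / 0.25 | 1.00–1.01 | 1.25 | 2.3–2.6% |
| 0.35 / 0.25 | 0.96–0.99 | 1.21–1.23 | 3.6–6.2% |
| 0.50 / 0.25 | 0.92–0.98 | 1.15–1.22 | 4.7–18.5% |

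The small departures in the first row are simulation noise.

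**The case against.** The strongest reply is that the protocol has several other routes to these events.

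- **Footnote [dd]** brings the questionnaire into the EOS assessment. Because it asks about events since the last study visit and records their dates, one EOS contact could cover the whole gap. This stands as a reading, but 7.5.2 and 9.3.12 mark only EOS status as compulsory. Sites hold both texts.
- **AE and SAE reporting** runs to global completion, and an MI or stroke leading to hospitalization is an SAE. This stands as a second route. It depends on the site becoming aware (10.3.3), and AE assessment is itself only optimal in 7.5.5.4.
- **Planned visits should continue** under 11.5. Section 10.1.1 (transplant) and Appendix A footnote [j] (pregnancy) say much the same for those groups. This conflicts with 7.5.5.4 and does not override it.
- **Any visit that takes place**, unscheduled ones included (9.3.11), carries the questionnaire. True, but nothing fixes that a visit takes place.
- **Vital status alone** is presented as the extreme case. True as intent, but the list that makes the questionnaire optional is not limited to that case.
- **The analysis censoring four weeks after discontinuation** (11.7.1) is largely protected. That stands, but it is not the primary analysis.

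A reader might infer that a site complies fully with the whole protocol by recording only that a subject is alive years later. The documents do not support that, given 10.3.1, 11.5 and footnote [dd]. A reader might also infer that the MACE result is biased in favour of vadadustat. The documents give no discontinuation rates, so neither the presence nor the direction of an arm difference is known.

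**Conclusion.** The point holds as a conflict in the text with a real ascertainment risk. From the four-week Follow-up visit onward, the sections that govern off-drug follow-up require only EOS status, while the MACE analysis counts all off-drug time.

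The size rests wholly on assumptions. With a non-fatal share of 25% to 45%, vital-status-only time of 20% to 30% against 15% to 20%, and every such event missed, the hazard ratio is multiplied by about 0.93 to 1.00. Partial capture through the other routes would shrink this. Equal discontinuation costs events but causes essentially no bias, and more stopping on darbepoetin reverses the direction. The false-noninferiority figures also assume that CI-0015 has the same gap; its protocol is not shown.

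This study's own MACE result is descriptive, but its events feed the pooled test. The 631-event calculation is correct. This is a change the sponsor should make, and it does not invalidate the design.

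**What to change.** In 7.5.2, 7.5.5.4, 9.3.12, the synopsis and Appendix A footnotes [c] and [dd]:

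1. Require the MACE Endpoint Questionnaire at a fixed interval after the Follow-up visit (for example every 12 weeks) and at EOS, for every off-drug subject who has not refused that contact. Allow it by visit, telephone, alternative contact or record review.
2. Keep vital status alone as the documented fallback for subjects who decline.
3. Record the date of the last MACE assessment, so that time in which nobody asked about MI or stroke can be told apart from event-free time. Section 11.7.1 censors at the last study assessment, and an EOS vital-status contact could be read as one.
4. Reconcile these sections with 10.3.1 and 11.5, so that sites have one rule.

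The cost is an amendment to wording and some site effort for contacts through channels that 7.5.5.4 already lists. No treatment rule changes, and no subject is held to more contact than they accept.
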